Prospective randomized control study of two different types of luteal phase support in natural cycle frozen embryo transfer (FET) and its effect on pregnancy rates

The ability to transfer frozen embryos makes it possible to keep frozen the amount of embryos created in in-vitro-fertilization (IVF) treatments for later use. Advantages of frozen embryos transfer (FET) include reduced embryo loss after IVF and a higher pregnancy rate. The rate of frozen embryos transfer has increased in recent years due to a higher tendency of single embryo transfer (SET), use of preimplantation genetic testing, and prevention of ovarian hyperstimulation (1,2). Due to developments of freezing technology and techniques in recent years, embryo freezing enables the advantages mentioned above without compromising the pregnancy rate (3).

There are different methods to prepare the endometrium for FET:

1. Natural cycle (NC) - Timing of ovulation by diagnosing the luteinizing hormone (LH) Surge. The advantage of a NC is the natural preparation of the body for implantation without the need for medicinal intervention. The disadvantage is need of intense monitoring to detect ovulation and inflexibility of day of embryo transfer. As a result, NC results in higher percentages of cycle cancellation.
2. Modified natural cycle (mNC) - Inducing ovulation by administration of Human Chorionic Gonadotropin (HCG) trigger. The advantage of ovulation induction with HCG is greater flexibility and ability to plan transfer day according to the availability of the system, with fewer visits by the patient.
3. Medical - preparation of endometrium with estrogen and progesterone. This method is suitable for women who do not ovulate regularly. This allows flexibility of the treatment with fewer cycle cancellations.

Studies that compared pregnancy outcomes of natural versus adapted NC are inconclusive (4-8). In recent years, several studies showed higher clinical pregnancy and ongoing pregnancy rates in NC group compared to group treated with HCG for ovulation induction (7-8).

Recently, several studies showed advantages of FET in NCs. A study published in April 2020 by XITONG LIU in Fertility and Sterility showed a higher rate of live births

and a reduced rate of miscarriages in NC FET group compared to the drug-treated group (9). Additional studies showed higher rates of gestational hypertension (10 - 11), macrosomia and post-term pregnancies in the medicated FET groups (10).

Endogenous progesterone secreted by the corpus luteum after natural ovulation is expected to provide an adequate luteal support as in spontaneous pregnancies. Therefore, it is assumed that there is no need for luteal support when embryos are transferred in NCs, and the benefit of medical luteal support is not conclusive (12-15). Nevertheless, a meta-analysis published in Human Reproduction in 2012, examined the effect of luteal support with progesterone and showed higher pregnancy rates in the group that received luteal support compared to those who did not receive it (16). It should be noted that most of the studies were performed with induction of ovulation by HCG.

Administration of HCG for luteal support is used both in fresh and frozen cycles. A previous study showed higher ongoing pregnancy rates in a group that received HCG within the day of natural LH surge together with vaginal progesterone from the day of embryo transfer compared to luteal support with progesterone alone. The use of 1500 units of HCG on cycle day 18 and 21 resulted with a significant increase in serum progesterone levels (17).

Administration of Gonadotropin Releasing Hormone (GnRH) analog as a treatment for luteal support in fresh IVF cycles has shown higher clinical pregnancy, multiple pregnancies, and live birth rates (18). When GnRH agonist is used (as single or repeated doses) it may cause an increase in LH secretion by the pituitary gland which augments the function of the corpus luteum and may lead to direct local stimulation of the endometrium [19].

In 2015, a retrospective cohort study from Israel compared the use of progesterone versus administration of HCG and GnRH agonist in NC FET. They showed a higher clinical pregnancy rate in the group treated with GnRH agonist and HCG (20). Another randomized prospective controlled showed that the addition of a GnRH agonist to luteal support with HCG compared with HCG alone in NC FET increased clinical pregnancy and implantation rates when frozen cleavage stage embryos were transferred (21). In 2016, a randomized prospective study from Finland examined the use of GnRH agonists in addition to standard vaginal progesterone support compared to a group treated with progesterone alone in 98 women undergoing NC FET (22). Both clinical and ongoing pregnancy rates were higher in the group treated

with GnRH agonists, but due to small sample size, the difference was not statistically significant.

It is important to note that GnRH agonists are not considered teratogenic (23). In over 340 women exposed to GnRH agonists in the mid-luteal phase, the rate of birth defects and miscarriages (2.5% and 15%, respectively) was similar to the general IVF population (24-26).

There is a need for further research to examine the effectiveness of GnRH agonist treatment as luteal support in in NCs FET. Conducting a prospective randomized controlled study will allow to determine the treatment efficacy of GnRH agonist and HCG in relation to the standard luteal support with progesterone.

The aim of the study is to compare the pregnancy rate between women treated with GnRH agonist together with HCG and standard luteal support with progesterone in the return of frozen embryos in natural cycles and in vitro fertilization treatments.

Primary outcome

- Clinical pregnancy rate – visualization of intrauterine gestational sac on ultrasound divided by number of transfers

Secondary outcomes

- Overall pregnancy rate - number positive bhCG divided by total number of transfers
- Ongoing pregnancy rate – visualization of fetal cardiac activity divided by total number of transfers
- Implantation rate – number of gestational sacs divided by number of embryos transferred
- Ectopic pregnancy rate – number of ectopic pregnancy divided by number of positive bhCG
- Miscarriage rate – number of non-viable before 24 weeks divided by total number of positive bhCG
- Live birth rate – number of live births after 24 weeks divided by number of transfers.

Study methods

Women who undergo natural cycle FET at the IVF center in Shaare Zedek Medical Center will be recruited.

During the visit to the clinic, the women's demographic and clinical data will be collected. The women who are found to be suitable according to the research criteria will receive an explanation of the nature of the study and will sign a consent form for participation in the study in accordance with the procedures of the Institutional Helsinki Committee.

The women can give an agreement until the ET day.

The number of embryos that will be returned will be determined according to the age of the woman, the number of treatment cycles and the quality of the embryos in accordance with the accepted policy in the unit.

The distribution of the patients to the two study groups will be done randomly by computer in a ratio of 1:1. Sealed envelopes containing information regarding the type of treatment for luteal support will be attached to the consent forms.

144 women will be divided into two groups, and each group will receive a different luteal treatment:

Study group – patients will receive luteal support of GNRH agonist and HCG according to departmental protocol:

Cleavage stage embryo:

- ET day (embryo day 2-3) - Ovitrelle 125mcg
- Day 3 after ET - Ovitrelle 125mcg + Decapeptyl 0.1mg
- Day 6 after ET - Ovitrelle 125mcg
- Day 9 after ET - Ovitrelle 125mcg

Embryo blastocyst stage:

- ET day (embryo day 5-6) - Ovitrelle 125mcg + Decapeptyl 0.1mg
- Day 3 after ET - Ovitrelle 125mcg
- Day 6 after ET - Ovitrelle 125mcg

Control group - patients will receive luteal support of vaginal progesterone – 100 mg Endometrin twice daily until week 8 of pregnancy.

Clinical pregnancy will be defined as the demonstration of an intrauterine gestational sac. Other pregnancy outcomes will be received in a telephone conversation with the patients and computer database nine months after the treatment.

Statistical calculations

Based on the clinical pregnancy rate in the prospective study by Bjuresten, et al [13], where a clinical pregnancy rate of 32% was found among women treated with progesterone for luteal support, and given an alpha of 5% and a power of 80%, 144 women (72 women in each group) are required in order to demonstrate a clinical pregnancy rate of 55% in the study group.

Comparison of categorical variables will be carried out using the CHI-SQUARE TEST. Comparison of continuous variables will be performed using the Students t-Test or Mann–Whitney U method depending on the variable distribution (normal vs. non-normal distribution, respectively). A multivariate regression will also be conducted in order to determine which variables are significantly and independently related. Statistical significance will be defined when P values are less than 0.05

Inclusion Criteria

- Normo-ovulatory women
- Women undergoing frozen embryos transfer in a natural cycle
- Age 18-45
- BMI 18-35

Exclusion Criteria

- Women undergoing medicated frozen embryos transfer
- Women with a BMI over 35 or under 18.
- Women with hydrosalpings

- Women with defects or uterine malformations (congenital) or acquired such as myomas

- Egg donation and surrogacy

- Use of preimplantation genetic testing

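### Minor, cheap improvement: the primary rate is counted per transfer while women are randomised and powered, and the plan gives neither an envelope-opening time nor a rule for an allocated woman without a transfer

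*Combined protocol and SAP*

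**What the plan says.** All places are in the combined protocol and SAP.

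- **Primary outcome.** Clinical pregnancy is defined as "visualization of intrauterine gestational sac on ultrasound divided by number of transfers". The denominator is transfers.
- **Statistical calculations.** The unit is women: "144 women (72 women in each group) are required in order to demonstrate a clinical pregnancy rate of 55% in the study group". The control assumption is worded as "a clinical pregnancy rate of 32% was found among women treated with progesterone for luteal support", which does not settle whether 32% is per transfer or per woman. The test for categorical variables is the chi-square test.
- **Study methods, allocation.** Women are randomised 1:1. "Sealed envelopes containing information regarding the type of treatment for luteal support will be attached to the consent forms". On consent: "The women can give an agreement until the ET day".
- **Study methods, treatment.** Both study-group schedules begin on the day of transfer and depend on embryo stage, for example "ET day (embryo day 2-3) - Ovitrelle 125mcg". Control treatment is "100 mg Endometrin twice daily until week 8 of pregnancy", which has an end but no start day.
- **Background, natural cycle.** The stated drawback is "need of intense monitoring to detect ovulation and inflexibility of day of embryo transfer", and the text links this to more cancelled cycles. It gives no rate.

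The plan does not state when the envelope is opened, which women form the analysis set, how an allocated woman without a transfer is counted, or that each woman contributes one transfer. It describes no masking.

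**The concern.** A woman who is allocated but has no transfer adds nothing to a numerator or a denominator counted in transfers. If her envelope was opened before transfer was certain, she leaves the primary comparison after randomisation, and the trial then compares women who reached transfer rather than the groups as randomised.

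The consequence depends on why she is lost. Loss unrelated to arm reduces precision and nothing else. Loss that differs between arms and is linked to the chance of conceiving can bias the comparison. With no masking described, a known allocation could influence the decision to go ahead.

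The same denominator has a second weakness. It does not limit a woman to one transfer, and the chi-square test assumes independent units, so two transfers from one woman should not both be counted.

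**Working it through.** **Inputs.** From Statistical calculations: 32% v 55%, alpha 5%, power 80%, 72 per arm. The plan does not state sidedness; two-sided is taken because it reproduces the stated size. The plan gives no share of women without a transfer, so d = 5% and 10% are assumptions.

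**1. The plan's own figure.** Pooled-variance formula with mean rate p̄ = (0.32 + 0.55)/2 = 0.435:

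n = [1.960·√(2·0.435·0.565) + 0.842·√(0.32·0.68 + 0.55·0.45)]² / 0.23² = (1.374 + 0.574)² / 0.0529 = 71.74, so 72 per arm and 144 in total. This reproduces.

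Power at 72 per arm = Φ[(0.23·√72 − 1.374)/0.682] = Φ(0.847) = 80.1% (81.0% by exact enumeration of the uncorrected chi-square test). So 144 is the size needed if every randomised woman has exactly one transfer; there is essentially no spare allowance.

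**2. Envelopes opened once transfer is certain, one transfer per woman.** Then d = 0, the two denominators coincide, and power is 80.1% either way.

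**3. Envelopes opened earlier, equal loss d in both arms, 32% and 55% taken as per-transfer rates.**

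- Current analysis: 72(1 − d) transfers per arm at 32% v 55%.
- Per woman randomised: 72 per arm at 0.32(1 − d) v 0.55(1 − d), with no transfer counted as not pregnant.

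| d (assumed) | Per-woman rates | Power, current per-transfer | Power, per woman | Cost of the fix |
|---|---|---|---|---|
| 0 | 32.0% v 55.0% | 80.1% | 80.1% | 0 |
| 5% | 30.4% v 52.25% | 78.1% | 76.4% | 1.6 points |
| 10% | 28.8% v 49.5% | 75.8% | 72.5% | 3.3 points |

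The last column is taken before rounding (78.06 − 76.44 and 75.80 − 72.52). The rest of the fall from 80.1% comes from losing women and arises under the current analysis too. With one woman per arm not transferred (d = 1/72), per-woman power is 79.1%. If 32% and 55% are already per woman randomised, per-woman power stays at 80.1%.

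**4. False-positive rate of the per-transfer analysis with no treatment effect.** The true rate is 32% in both arms, tested with the uncorrected chi-square test at two-sided 5%, by exact enumeration.

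| Transfers analysed | Situation | Rates compared | False-positive rate |
|---|---|---|---|
| 72 v 72 | No loss | 32% v 32% | 5.0% |
| 68 v 68 | Equal 5% loss, unrelated to outcome | 32% v 32% | 5.2% |
| 65 v 65 | Equal 10% loss, unrelated to outcome | 32% v 32% | 5.2% |
| 72 v 68 | One arm only, 5%, all non-conceivers | 32% v 0.32/0.95 = 33.7% | 5.6% |
| 72 v 65 | One arm only, 10%, all non-conceivers | 32% v 0.32/0.90 = 35.6% | 7.2% |

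The 5.2% values reflect the discreteness of the test, not bias. The extreme cases shift the affected arm's rate by 1.7 or 3.6 points, against a planned difference of 23. Exact results are not smooth in n, so small differences should not be over-read.

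**The case against.** The strongest reply is that the trial's own schedule makes the problem unlikely. Study-group treatment begins on ET day and depends on embryo stage, the envelope holds only the type of luteal support, and the inclusion criteria describe women undergoing transfer. Nobody needs the allocation much before transfer. The causes of cancellation named in the background arise before any study-group dose, so they cannot be effects of that treatment. Four of the seven listed outcomes use transfers as the denominator, and a per-transfer rate is defensible for support of this kind if allocation is revealed only when transfer is certain.

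Most of this stands, and it is why the point is minor. It does not close the gap. The plan does not require late opening, and because control progesterone has no stated start day, an earlier opening is not excluded.

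A reader might infer something stronger: that the trial will lose randomised women, or that its primary result will be biased. The documents do not support that. They give no cancellation rate for this trial, show no woman being allocated and then cancelled, and give no sign that loss would differ by arm. Bias would need early opening together with loss that is both unequal and linked to prognosis. Unequal loss would in turn need someone acting on a known allocation, or control treatment starting before ET.

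It is also fair to say that when loss is unrelated to arm, a per-woman analysis removes no bias and gives up some power.

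**Conclusion.** The point holds as a minor, cheap improvement. The mismatch between transfers counted and women randomised is in the text, and so is the absence of an opening time and a counting rule. On the likelier reading, opening at or near transfer with one transfer per woman, the effect is close to nil.

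On the less likely reading, equal loss leaves the false-positive rate near 5% and lowers power. The extreme one-arm case reaches 5.6% or 7.2%. Those figures rest on assumed losses of 5% and 10%, confined to one arm and made up entirely of women who would not have conceived; they bound the risk rather than predict it. The power figures assume equal loss and that 32% and 55% are per-transfer rates.

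**What to change.** 1. Make the primary analysis clinical pregnancy per woman randomised, in her assigned arm, with no transfer counted as not pregnant. Keep the per-transfer rate as a secondary outcome.
2. Count one transfer per woman, named in advance (for example the first study transfer), so that the chi-square test is applied to independent units.
3. State when the envelope is opened, preferably as close to the transfer as the treatment schedules allow. Reconcile this with the start day of control progesterone, which the plan does not give.
4. State whether 32% and 55% are per transfer or per woman, and that 144 carries essentially no allowance for women without a transfer.

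**Cost.** Protocol wording only; no extra enrolment is proposed. If every woman has exactly one transfer, the two analyses are identical and nothing is lost. Otherwise, if 32% and 55% are per-transfer rates, the change itself gives up 1.6 points of power at an assumed 5% equal loss and 3.3 points at 10%. If control treatment turns out to require earlier opening, item 1 is what keeps the comparison between the groups as randomised.

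### Overall pregnancy counts any positive bhCG, but only the study arm is given hCG after transfer, so the written rule can count residual drug as pregnancy in that arm alone (minor)

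*Combined protocol and SAP*

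**What the plan says.** Under Secondary outcomes the combined protocol and SAP defines "Overall pregnancy rate - number positive bhCG divided by total number of transfers". The same count is the denominator of two further secondary outcomes: ectopic pregnancy is "number of ectopic pregnancy divided by number of positive bhCG", and miscarriage is "number of non-viable before 24 weeks divided by total number of positive bhCG".

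Under Study methods, in the study group "patients will receive luteal support of GNRH agonist and HCG according to departmental protocol". The listed hCG injections fall on transfer day and days 3, 6 and 9 for cleavage-stage embryos, the last being "Day 9 after ET - Ovitrelle 125mcg". For blastocysts they fall on transfer day and days 3 and 6, the last being "Day 6 after ET - Ovitrelle 125mcg". In the control group "patients will receive luteal support of vaginal progesterone", and no hCG is listed.

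On follow-up, the plan says "Other pregnancy outcomes will be received in a telephone conversation with the patients and computer database nine months after the treatment". It gives no day for the bhCG test, no cut-off, no interval after the last injection and no rule for confirming or reclassifying a positive.

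**The concern.** The substance that defines the outcome is also a drug given in one arm only. If the test is read before the drug has cleared, a non-pregnant woman in the study arm can be counted as pregnant; post-transfer treatment cannot do this to a control woman. Randomisation does not protect against this, because the source of the misreading is the assigned treatment itself.

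Any error in overall pregnancy would favour the study arm. The ectopic and miscarriage rates would be distorted through their denominator. For miscarriage the numerator may be affected too, because the wording does not say whether a positive test that later falls with no sac seen is a non-viable pregnancy. Three of the six secondary outcomes therefore depend on the undefined reading.

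**Working it through.** **The plan's own figure.** The inputs in Statistical calculations are 32% against 55%, alpha 5% and power 80%. The two-sided formula with pooled variance and no continuity correction is

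n = [1.960·√(2·0.435·0.565) + 0.842·√(0.32·0.68 + 0.55·0.45)]² / 0.23² = 71.7.

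This rounds up to 72 per arm, 144 in all, with power 80.1%. It matches the plan. It concerns clinical pregnancy, which is read from ultrasound, so nothing below changes it.

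**Effect on overall pregnancy.** Let p be the true rate, equal in both arms, and f the share of non-pregnant study-arm women with a drug-derived positive. The study arm then reads p + (1 − p)f and the control arm reads p. The documents do not give f, so the values are assumed. The chance of P<0.05 is from exact binomial enumeration of the uncorrected chi-square test, 72 per arm.

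| f | Study rate, p = 40% | Chance of P<0.05: p = 32% | p = 40% | p = 55% |
|---|---|---|---|---|
| 0 | 40% | 5.0% | 5.1% | 5.4% |
| 5% | 43% | 7.0% | 6.7% | 6.2% |
| 10% | 46% | 13.3% | 11.7% | 8.8% |
| 20% | 52% | 38.8% | 31.6% | 19.8% |

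For example, at p = 40% and f = 20%: 0.40 + 0.60·0.20 = 0.52.

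**Effect on miscarriage.** Take p = 40% and a true loss rate of 15% per positive; 15% is the figure quoted in the background for women exposed to a GnRH agonist. Among 72 women there are 28.8 true positives, 4.32 losses and 43.2 non-pregnant women. At f = 20%, 43.2·0.20 = 8.64 women are misread.

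- Drug positives not counted as losses: 4.32 / (28.8 + 8.64) = 11.5%.
- Drug positives counted as losses: (4.32 + 8.64) / (28.8 + 8.64) = 34.6%.

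At f = 5% and 10% the first coding gives 14.0% and 13.0%, and the second gives 20.9% and 26.1%. The direction therefore depends on a coding choice that the plan does not state.

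**Effect on ectopic pregnancy.** At an assumed true rate of 2% there are 0.576 expected events in the arm. At f = 20% the rate reads 0.576 / 37.44 = 1.5%.

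**Can f be narrowed by modelling clearance?** Not from these documents. Take the level on day t as the sum over injections of peak × 0.5^((t − injection day)/half-life). Assume peaks uniform on 30 to 100 IU/L, half-lives uniform from 24 h up to a cap, and a cut-off of 5 IU/L. The share of non-pregnant study-arm women still positive is then:

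| Day after transfer | Cap 36 h | Cap 42 h | Cap 48 h |
|---|---|---|---|
| Cleavage, day 16 | 0.1% | 12.8% | 29% |
| Cleavage, day 17 | 0% | 1.4% | 13% |
| Blastocyst, day 14 | 0% | 1.1% | 12% |

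The day on which the model shows no residual drug is set by the assumed cap. Peak, half-life, cut-off and test day are all assumptions. The documents also do not give the mix of cleavage and blastocyst transfers, so these shares cannot be turned into a value of f for the whole arm.

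**The case against.** The strongest reply is that no error has been shown. The plan omits a test day but contradicts none of its own figures. The study regimen follows a departmental protocol that is not among the documents and may fix a late enough test. The clearance assumptions have no source in the plan. The outcome is secondary, and the primary outcome does not use bhCG.

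Most of this stands, and it limits the point. A reader might infer that overall pregnancy will be inflated in this trial; the documents do not support that, because actual test timing is unknown. A reader might also take a clearance model as showing that a given day is safe, or that only early tests matter. The table above shows that such a conclusion follows from the assumed half-life limit. Nor can one say that miscarriage would be only slightly diluted, since that holds under one coding and reverses under the other.

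What the reply does not remove is the rule itself. As printed, any positive counts, and one arm is given the substance being measured. If local practice already avoids the problem, writing it into the definition costs little.

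A pre-transfer hCG trigger, which the introduction describes for modified natural cycles, is not an answer either way: it is not part of the allocated treatment and so would not be specific to one arm.

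**Conclusion.** The point holds as a minor one. The definition of overall pregnancy is open to arm-specific misclassification, and the ectopic and miscarriage rates inherit it through their denominator. That rests on the printed definitions and regimens, and on reading Ovitrelle as the hCG component, which the study-group description supports.

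The size is unknown. The 7%, 12% and 32% chances of a nominally significant result at a true rate of 40% are illustrations for assumed misreading of 5%, 10% and 20%; they do not estimate what will happen. For miscarriage, even the direction is unsettled: a true 15% could read 12% or 35% at 20% misread, depending on coding.

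A reader might extend the concern to the main result. The documents do not support that: clinical pregnancy, ongoing pregnancy, implantation and live birth are defined by sac, cardiac activity or birth, and the sample size of 144 is based on clinical pregnancy.

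**What to change.** 1. Define positive bhCG for the outcome with one cut-off and, within each embryo stage, the same reading day in both arms. Set that day relative to the last scheduled hCG injection of the study regimen at that stage, using routine tests where their timing allows.
2. Flag as unconfirmed any positive with no later ultrasound confirmation or ectopic diagnosis. Apply the rule identically in both arms and do not let it depend on optional repeat tests, which could be ordered more often in hCG-treated women. Report overall pregnancy with and without unconfirmed positives, and do not count them as miscarriages.
3. As a sensitivity analysis, report miscarriage and ectopic pregnancy per confirmed pregnancy (ultrasound-confirmed or diagnosed ectopic) beside the planned rates, and list losses known only from bhCG separately.

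The cost is some rewording, one data flag and a small extra analysis, with no extra patients. The confirmed version drops some genuine very early losses and lies close to the primary outcome plus ectopics, which is why both versions are shown. If routine testing is too early for item 1, rely on items 2 and 3. This changes how the outcome is measured and reported; no change to the treatment schedule is implied.

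### Ectopic pregnancy and miscarriage are compared only among women with a positive bhCG, so neither outcome has a planned randomised comparison

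*Combined protocol and SAP*

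**What the plan says.** The list under Secondary outcomes has two entries whose denominator is the number of positive pregnancy tests: "Ectopic pregnancy rate – number of ectopic pregnancy divided by number of positive bhCG" and "Miscarriage rate – number of non-viable before 24 weeks divided by total number of positive bhCG".

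The positive test is also an outcome compared between the arms: "Overall pregnancy rate - number positive bhCG divided by total number of transfers". Clinical pregnancy (the primary outcome) and ongoing pregnancy are per transfer too, as is live birth: "Live birth rate – number of live births after 24 weeks divided by number of transfers". Implantation is per embryo transferred.

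Statistical calculations sizes the trial on a large difference in pregnancy. It takes from a cited prospective study that "a clinical pregnancy rate of 32% was found among women treated with progesterone for luteal support", and states that 144 women, 72 per group, "are required in order to demonstrate a clinical pregnancy rate of 55% in the study group". Categorical variables are to be compared by chi-square at the 0.05 level, and a multivariate regression is mentioned without a specified outcome or covariates. The plan contains no comparison of ectopic pregnancy or miscarriage per woman or per transfer.

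**The concern.** Randomisation makes the two groups of 72 women comparable. It does not make the women with a positive test comparable, because becoming positive may depend on the treatment. If the study regimen produces pregnancies that would not have begun under progesterone, the study arm's positive group contains women with no counterpart in the control arm's positive group. The chi-square on the per-bhCG rates then mixes any effect on ectopic pregnancy or miscarriage with the difference in who became pregnant.

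What is at stake is how these two estimates are read. Equal numbers of ectopics per woman can appear as a lower rate in the study arm, and more miscarriages per woman can appear as no difference.

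**Working it through.** **Inputs.** Control and study clinical pregnancy rates of 32% and 55%, alpha 5%, power 80% and 72 per group come from Statistical calculations. The 15% miscarriage figure is in the background paragraph on GnRH agonist exposure and is used only as an illustration. Assumptions of this check: every randomised woman has one transfer, so per woman and per transfer coincide; two ectopics occur in each arm (the documents give no ectopic rate); and the 15% applies per positive test.

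**Plan's own figure.** The plan does not state sidedness. Two-sided, with pooled variance and no continuity correction, the mean rate is (0.32 + 0.55)/2 = 0.435 and

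n = [1.96 × √(2 × 0.435 × 0.565) + 0.8416 × √(0.32 × 0.68 + 0.55 × 0.45)]² / 0.23² = (1.374 + 0.574)² / 0.0529 ≈ 71.7, rounded up to 72.

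The stated 72 per group is reproduced.

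**Relation between the two scales.** Let the conditional rate be events per positive test. Then

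events per woman = conditional rate × positive-test rate,

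so the per-woman ratio equals the conditional ratio times the ratio of positive-test rates. The two ratios agree only if the positive-test rates are equal.

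**Minimum number of positive tests.** Every clinical pregnancy implies a positive test: 72 × 0.55 = 39.6 (about 40) and 72 × 0.32 = 23.04 (about 23). Clinical pregnancy requires an intrauterine sac, so ectopics come on top of these counts.

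**Ectopic pregnancy, two per arm.**
- Per woman: 2/72 = 2.8% in each arm, ratio 1.00.
- As planned: 2/(40 + 2) = 4.8% against 2/(23 + 2) = 8.0%, ratio 25/42 = 0.60.
- Chi-square without correction: 67 × (2 × 23 − 40 × 2)² / (42 × 25 × 4 × 63) = 0.29, p about 0.59.

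**Miscarriage, 15% per positive test in both arms.**
- As planned: 15% against 15%, ratio 1.00.
- Expected losses: 0.15 × 39.6 = 5.9 against 0.15 × 23.04 = 3.5.
- Per woman: 0.15 × 0.55 = 8.25% (8.3%) against 0.15 × 0.32 = 4.8%, ratio 0.55/0.32 = 1.72.
- Difference: 3.45 percentage points, with standard error √[(0.0825 × 0.9175 + 0.048 × 0.952)/72] = 4.1 points. The approximate 95% interval is −4.6 to 11.5 points, and the power to detect this difference is about 13%.

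**Range for the missing positive-test rate.** Suppose each arm has extra positive tests without a clinical pregnancy, with any ectopics among them.

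| Extra positive tests per arm | Positive-test rates, study and control | Per-woman miscarriage ratio at equal 15% | Two ectopics per arm, as planned |
|---|---|---|---|
| 5 points | 60% and 37% | 0.60/0.37 = 1.62 | 2/43 = 4.7% against 2/27 = 7.4% |
| 10 points | 65% and 42% | 0.65/0.42 = 1.55 | 2/47 = 4.3% against 2/30 = 6.7% |

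If treatment turned more positive tests into clinical pregnancies without raising the number of positive tests, the positive-test rates would be equal and the two scales would not diverge.

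**The case against.** The strongest reply has four parts.

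- **The per-transfer figure can be recovered.** The overall pregnancy rate is a planned outcome, and multiplying it by the conditional rate gives events per transfer exactly, for example 42/72 × 2/42 = 2/72. Live birth per transfer already shows the net result. This stands. A reader might infer that benefit and loss cannot be related to each other under this plan, and the documents do not support that. What is missing is a stated per-woman comparison with its interval.
- **The per-bhCG rate answers a real question.** Once pregnant, is loss more likely? A woman who does not conceive cannot miscarry, so per-woman loss rises simply because more women conceive. This stands too, and it is a reason to show both rates and not to discard the conditional one.
- **No test result would change.** A reader might infer that the plan would declare protection against ectopic pregnancy. It would not: p is about 0.59 in the illustration, and the per-woman comparison is also weak at this size. With so few events, however, readers depend on estimates and intervals, and those do depend on the denominator.
- **The size rests on an input that is not given.** Without a positive-test rate the divergence is conditional on assumptions. This is correct, and the results above are therefore a range.

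**Conclusion.** The point holds as a matter of estimation and interpretation. As planned, ectopic pregnancy and miscarriage are compared only within a post-randomisation group that is likely to differ between arms if the trial's own assumption is met, and no randomised comparison of either outcome is specified.

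In the illustrations, equal ectopics per woman appear as a ratio of about 0.60, and equal miscarriage risk per positive test corresponds to 1.55 to 1.72 times as many losses per woman. These figures rest on the 55% and 32% design rates, on 72 women with one transfer per arm, and on an assumed positive-test rate. They shrink to no divergence if treatment does not raise positive tests.

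The primary outcome and its conclusion are not affected. A reader might also suspect that hCG given after transfer in the study arm inflates its positive tests. The documents state neither the day nor the threshold of the bhCG test, so they do not establish this, and the point does not depend on it.

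**What to change.** Add to Secondary outcomes a between-arm comparison of ectopic pregnancy and of miscarriage per woman randomised, or per transfer as for the primary outcome. Report counts, the difference and its 95% confidence interval. Keep the rate per positive bhCG beside it, labelled as conditional on pregnancy and not protected by randomisation.

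The cost is two lines in the outcome list and two table rows, with no new data. The drawback is that losses per woman can look higher in the arm with more pregnancies, so the text should say that both rates are to be read together with live birth per transfer.
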